## 2.3 Risk / Benefit Assessment

The potential benefits to participants and society are likely to outweigh the minimal risks from participation in the study.

### 2.3.1 Potential Risks

Confidentiality. Participation in research may involve loss of privacy. Participants' records will be handled as confidentially as possible. All research records will be coded with a four-digit study identification (ID) code. Only the study investigators and their staff will have access to study records and test results. Study charts will be kept in a locked file cabinet in a locked office. Electronic data will be protected with a password and kept on a secure network. All collaborators will receive specimens only identified by the four-digit study ID. No individual identities will be used in any reports or publications resulting from this study.

Phlebotomy. Drawing blood from a vein may cause some discomfort, bleeding, or bruising where the needle enters the skin, and rarely, fainting or infection may occur. No more than 500 mL (2 cups) of blood will be drawn over any two-month period. This is within Red Cross guidelines. The total amount of blood allowable will take into account blood drawn as part of both LIINC and outSMART-LC. Risks of blood collection include anemia (low blood counts). Symptoms of anemia include tiredness, weakness, and dizziness. Participants will be checked for signs and symptoms of anemia at each visit, and CBC/diff will be checked as outlined in the schedule of events. If the investigator feels that a participant is at significant risk for anemia, the amount of blood collected will be reduced.

Nasal or oral swab. These collections may cause temporary discomfort.

Viral testing. Testing for viruses such as SARS-CoV-2, HIV and viral hepatitis and testing may be performed as part of this study. Being tested for these infections may cause anxiety, regardless of the test results. Receiving a positive test result may cause a lot of anxiety. If the test result is negative, there is still the possibility that a participant could be infected and test positive at some time in the future. In addition, there is always the rare possibility that the test results could be wrong. Newly positive test results for SARS-CoV-2, HIV, hepatitis B, hepatitis C, and Tuberculosis (TB) infections are required to be reported to the Department of Public Health.

Drug side effects. Possible side effects may include:

- 1) Allergic reactions. Allergic/hypersensitivity reactions can happen during and after infusion. Participants may experience the following signs and symptoms of allergic reactions: fever, chills, nausea, headache, shortness of breath (SOB), low or high blood pressure (BP), rapid or slow heart rate (HR), chest discomfort or pain, weakness, confusion, feeling tired, wheezing, swelling of lips, face, or throat, rash including hives, itching, muscle aches, feeling faint, dizziness and sweating. These reactions may be severe or life threatening. For this reason, participants will be monitored for at least 120 minutes after the delivery of AER002 vs placebo on Day 0.

- 2) Cytokine Release Syndrome (CRS). CRS is an acute systemic hyperinflammatory syndrome that can occur during and after infusion. Participants may experience the following symptoms:

fever, chills, nausea, vomiting, fatigue, body aches, headache, cough, low BP, skin rash, confusion, delirium, edema, SOB, rapid or slow HR, chest pain or discomfort, weakness, difficulty swallowing, diarrhea, dizziness, and joint pain. These reactions may be severe or life threatening. For this reason, participants will be monitored for at least 120 minutes after the delivery of AER002 vs placebo on Day 0.

- 3) Worsening symptoms after treatment. Participants may experience new or worsening symptoms after infusion, including fever, difficulty breathing, rapid or slow heart rate, tiredness, weakness, or confusion.
- 4) Local infusion-related site reactions. The side effects of getting any medicine by vein (IV infusion) may include brief pain, erythema, burning, itching, tingling, stinging, bleeding, bruising of the skin, soreness, swelling, skin necrosis, and possible infection at the infusion site.
- 5) Unanticipated AEs. These are not all the possible side effects.

### **2.3.2 Protection Against Risk**

Confidentiality. Participants' records will be handled as confidentially as possible. Participants will be assigned a unique four-digit study ID code that will appear on all specimens and in our database. All biologic specimens and clinical data obtained from this study will be linked to this code and not to personal identifying information (e.g., name, social security number, medical record number). A key which will link the four-digit code to the personal information will be maintained on a secure server only accessible to designated study staff and maintained by the PI. Lab personnel and database programmers will have access only to the coded number and the participant's date of birth; no other personal identification information will be available to them. Collaborators will receive specimens only identified by the four-digit study ID. No individual identities will be used in any reports or publications resulting from this study.

Phlebotomy. Relevant personnel are trained and certified phlebotomists. We will stay within Red Cross Guidelines of less than 500 mL every two months. Participants will be checked for signs and symptoms of anemia at each visit, and CBC/diff will be checked as outlined in the schedule of events. If the investigator feels that an individual is at significant risk for anemia, the amount of blood collected will be reduced. If the study participant's hemoglobin falls below 9 grams/deciliter (g/dl) or HCT falls below 27%, we will draw 5 mL of blood to check safety labs such as Hgb and HCT. Other than the blood required to check safety labs, the participant will not have more blood drawn until the Hgb rises above 9 g/dl or the HCT rises above 27%.

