14. Severe coagulopathy that would prevent an infusion (international normalized ratio ((INR) >2.0, history of hemophilia).
15. Severe anemia (hemoglobin <9 grams/deciliter (g/dL)).

16. Moderate or severe immunocompromise, according to the current NIH COVID-19 Treatment Guidelines as of March 6, 2023. The detailed list is in Appendix 2, and includes the following: (a) receiving active treatment for solid tumor or hematologic malignancy, including use of systemic chemotherapy for treatment of cancer within the year prior to screening, (b) prior solid-organ transplant with active immunosuppressive therapy, (c) CAR-T cell therapy or hematopoietic cell transplant, on immunosuppressive therapy or transplant within the prior 2 years, (d) primary immunodeficiency syndromes, (e) advanced or untreated HIV infection (see above), (f) on active high-dose corticosteroids (i.e.,  $\geq$  20mg prednisone or equivalent daily per day for  $\geq$  2 weeks).
17. Known prior diagnosis of myalgic encephalomyelitis/chronic fatigue syndrome (ME/CFS), preceding and not related to SARS-CoV-2 infection and not worsened since SARS-CoV-2 infection.
18. Known prior diagnosis of dysautonomia, preceding and not related to SARS-CoV-2 infection and not worsened since SARS-CoV-2 infection.
19. History of anaphylaxis or hypersensitivity upon receiving IV antibody infusions in the past.
20. Known allergy to any components used in the formulation of the intervention.
21. History of anaphylaxis or similar significant allergic reaction to prescription or non-prescription drugs or food products. Similarly, presence of severe atopic conditions as assessed by the PI represents significant risk for allergic reaction.
22. Pregnant, breastfeeding, or unwilling to practice birth control abide by the contraception requirements outlined in the inclusion criteria.
23. Participation in a clinical trial with receipt of an investigational product within 28 days or 5 half-lives (whichever is longer) prior to planned Day 0. For PET tracers specifically, which have a short half-life and are not biologically active outside this window, elapse of 5 half-lives prior to the planned D0 infusion is sufficient.
24. Current alcohol or illicit drug use as determined by the investigator to preclude participation.
25. Presence of a condition or abnormality that in the opinion of the Investigator would compromise the safety of the patient or the quality of the data.

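### The hold on research blood draws can be released while hemoglobin or hematocrit still meets the condition that started it

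*Combined protocol and SAP*

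**What the plan says.** The phlebotomy paragraph of protocol section 2.3.2 sets the only numerical stop on blood collection after enrollment that depends on the participant's blood count. The trigger reads "hemoglobin falls below 9 grams/deciliter (g/dl) or HCT falls below 27%, we will draw 5 mL of blood to check safety labs"; hemoglobin and hematocrit are named as examples of these tests. The hold exempts safety samples ("Other than the blood required to check safety labs") and lasts as follows: "the participant will not have more blood drawn until the Hgb rises above 9 g/dl or the HCT rises above 27" percent.

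The surrounding protections are:

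- Section 2.3.2, at the investigator's judgment: "If the investigator feels that an individual is at significant risk for anemia, the amount of blood collected will be reduced".
- Section 2.3.1, a cap that counts blood from both LIINC and this trial: "No more than 500 mL (2 cups) of blood will be drawn over any two-month period".
- Sections 2.3.1 and 2.3.2, a check for signs and symptoms of anemia at every visit.
- Section 6.3, criterion 15, which excludes at entry "Severe anemia (hemoglobin <9 grams/deciliter (g/dL". It sets no hematocrit limit.

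Appendix 1 schedules a CBC at Screening, D0 and D15 only. Biospecimen storage and research assays continue at D30, D90, D180 and D360.

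**The concern.** A hold that starts when either of two values is low is properly undone only when neither is low. The opposite of *A low or B low* is *A not low and B not low*. Here the release repeats the *or*, so recovery of one value is enough even if the other is still below its cut-off.

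What is at stake is participant safety. The error fails in the unsafe direction: research draws could restart in someone whose hemoglobin the protocol itself labels severe anemia and would not have admitted at entry.

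**Working it through.** **Inputs.** All cut-offs come from protocol section 2.3.2.

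- Start = (Hgb < 9) or (HCT < 27)
- Release as written = (Hgb > 9) or (HCT > 27)
- Release as it should read = (Hgb > 9) and (HCT > 27)

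**Worked pairs.**

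| Hgb (g/dl) | HCT (%) | Start met | Release as written | Release with *and* |
|---|---|---|---|---|
| 8.6 | 26.0 | yes | no | no |
| 8.7 | 27.5 | yes | **yes** | no |
| 9.3 | 26.5 | yes | **yes** | no |
| 8.7 | 27.2 | yes | **yes** | no |
| 9.2 | 27.6 | no | yes | yes |

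Every pair that straddles the cut-offs meets both conditions as written. None does with *and*.

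**Check over a grid.** Take Hgb 7.0 to 11.0 and HCT 21.0 to 33.0 in steps of 0.1.

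- All pairs: 41 × 121 = 4,961.
- Pairs that do not start the hold (Hgb at least 9.0 and HCT at least 27.0): 21 × 61 = 1,281.
- Pairs that start it: 4,961 − 1,281 = 3,680.
- Of these, pairs that also meet the release as written: 20 × 60 (Hgb low, HCT above) + 20 × 60 (Hgb above, HCT low) = 2,400.
- Of these, pairs that meet the release with *and*: 0.

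These counts test the logic only. They are not frequencies, since many grid pairs are physiologically implausible.

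**The more generous reading.** The verbs describe movement, so the release may mean that the value that fell must rise again. Under that reading 8.7/27.5 stays on hold, because only hemoglobin fell. But take a participant at 8.6/26.0, where both values fell. A recheck at 8.7/27.2 satisfies the hematocrit limb, because hematocrit fell and has risen above 27%. Hemoglobin at 8.7 still meets the start condition.

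**How wide the overlap can be.** The cut-offs stand in the ratio 27/9 = 3.0. For a participant with HCT/Hgb ratio r, the values straddle when Hgb lies between 9 and 27/r. The documents give no ratio, so 2.8 to 3.2 is an assumption.

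- r = 3.2: 27/3.2 = 8.44, so Hgb 8.44 to 9.00 with HCT above its cut-off.
- r = 3.0: no overlap.
- r = 2.8: 27/2.8 = 9.64, so Hgb 9.00 to 9.64 with HCT below its cut-off.

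**The case against.** The strongest reply is that the natural reading is dynamic. A hematocrit that never fell cannot rise above 27%, so the straddling examples and the grid count, which use static inequalities, overstate the problem. For the straddling case this is fair. What then remains is the case where both values are low and only one recovers. There one can still argue that the start condition applies to the recheck sample and nothing gives the release priority, so the text is unclear rather than permissive. That too is fair, but a safety rule that orders stop and go on the same sample still needs correcting.

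The second reply is that reach and excess risk are small, and this stands in full. About 30 participants are planned, hemoglobin below 9 is excluded at entry, and LIINC eligibility requires no chronic anemia (section 6.2, criterion 2). Only the D0 and D15 CBCs are scheduled trial samples that could start a hold after Screening. Within the assumed ratios, the lowest hemoglobin that could be released on hematocrit is 8.44, which is 0.56 g/dl below the cut-off.

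The third reply is that other protections remain, and that volume must be reduced once the investigator judges the anemia risk significant. They are real but do not replace an objective rule. The reduction depends on judgment, and the cap limits volume whatever the blood count. The symptoms listed in section 2.3.1 (tiredness, weakness, dizziness) overlap with qualifying Long COVID symptoms in section 6.2. After D15 no further CBC is scheduled; unscheduled repeats are at the investigator's discretion (section 10.6).

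The last reply is that *and* could cost samples from a participant with a stable discordant pair such as 9.3/26.5, which matters with 10 on placebo. But in that pair hematocrit is the value that fell, so the dynamic reading holds those samples too.

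**Conclusion.** The concern holds. The release is wrong as written under the literal reading, and under the dynamic reading it still fails when both values were low and one recovers. This follows from the text alone and needs no assumption. The size does need one: the hemoglobin window of about 8.44 to 9.64 g/dl assumes HCT/Hgb ratios of 2.8 to 3.2, and the number of participants affected cannot be derived from the documents, though it is likely to be very small. No endpoint, randomization or statistical result is affected. It is a minor wording error in a participant-safety rule. It should be corrected because it fails in the unsafe direction and the correction is nearly free.

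**What to change.** In section 2.3.2, reword the release so that draws resume only once hemoglobin is above 9 g/dl *and* hematocrit is above 27%. Leave both thresholds, the trigger, the 5 mL recheck and the exemption for safety samples as they are. No pair of values can then meet both start and release.

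The cost is a few words in a clarification letter or the next amendment, and possibly some deferred research draws. For a participant held on the D15 CBC, these are at most the draws at the four later trial visits (D30, D90, D180, D360), plus any LIINC draws in that time.

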## 6.2 Inclusion Criteria

1. Male, female, or transgender  $\geq 18$  years of age at Screening.
2. Enrolled or willing to enroll and complete at least 1 visit in the UCSF Long-term Impact of Infection with Novel Coronavirus (LIINC) study. Any adult who has been infected with SARS-CoV-2 or has ever received or is eligible to receive a SARS-CoV-2 vaccination, does not have chronic anemia, and who is able to provide written informed consent, is eligible to participate in LIINC.
3. History of confirmed acute SARS-CoV-2 infection, whose initial infection meets criteria as outlined below:
  - a. Report of a positive nucleic acid amplification test (NAAT) and/or a positive SARS-CoV-2 antigen rapid diagnostic test (RDT). Written proof of the test will be requested but is not required as long as the participant attests to the positive test.

AND

  - b. Long COVID (see below) attributed to SARS-CoV-2 infection with a variant against which AER002 is known to have neutralizing activity. In cases in which the variant is not

known from prior viral sequencing (most cases), the SARS-CoV-2 infection to which Long COVID is attributed should have been dated prior to August 15, 2022.

Note: For individuals who may be chronically infected, a genotype is required to confirm that they have a AER002-susceptible variant.

4. Clinical evidence of Long COVID, as confirmed by the investigator's assessment.

- a. At least two symptoms (see list) that are new or worsened since the time of SARS-CoV-2 infection, not known to be attributable to another cause upon assessment by the PI. At least two symptoms from those listed here must be present: systemic symptoms (e.g., fatigue, chills, post-exertional malaise), neurocognitive symptoms (e.g., trouble with memory/concentration ("brain fog"), headache, dysautonomia/postural orthostatic tachycardia syndrome, dizziness, unsteadiness, neuropathy, sleep disturbance), cardiopulmonary symptoms (e.g., chest pain, palpitations, shortness of breath, cough, fainting spells), musculoskeletal symptoms (e.g., muscle aches, joint pain), gastrointestinal symptoms (e.g., nausea, diarrhea). Although other symptoms (e.g., skin rash, hair loss, mental health symptoms, trouble with smell/taste, genitourinary symptoms) will be recorded and tracked, at least two core symptoms listed above must be present. Note: the two symptoms can be from within the same category (for example, brain fog and headache).

AND

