## **9 STUDY PROCEDURES AND GUIDELINES**

A Schedule of Events representing the required testing procedures to be performed for the duration of the study is diagrammed in Appendix 1. The Schedule of Events will serve as the final resource for guiding study activities.

Prior to conducting any study-related activities, written informed consent and the Health Insurance Portability and Accountability Act (HIPAA) authorization must be signed and dated by the subject or subject's legal representative. If appropriate, assent must also be obtained prior to conducting any study-related activities.

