## APPENDIX 1. SCHEDULE OF EVENTS

Target Day	-28	-7	0	1	15	30	90	180	360
Visit Name	Screen	Baseline	Intervention	Phone FU	2W	1M	3M	6M	12M
Visit Window	-28 to -8	-21 to -1	N/A	+1	+/-3	+/-5	+/-14	+/-14	+/-28
Screening Procedures									
Informed Consent	x								
Eligibility Review	x								
Screening Labs	x								
Demographics	x								
Medical History (inc. ME/CFS, hEDS, EM, MCAS assess.)	x								
COVID-19 History	x								
Concomitant Medications	x	x	x	x	x	x	x	x	x
Study Product Administration									
Randomization			x						
AER002 vs Placebo			x						
Clinical Assessments									
Vital Signs	x	x	x 		x	x	x	x	x
Physical Assessment	x	PRN	PRN		PRN	PRN	PRN	PRN	PRN
Long COVID Symptom Assessment (LIINC Quest.)	x	x	x		x	x	x	x	x
Quality of Life, (e.g., EuroQoL)	x	x			x	x	x	x	x
PROMIS-29	x	x			x	x	x	x	x
PGIC Scale						x	x	x	x
Duke Activity Status Index	x	x			x	x	x	x	x
Post-COVID Functional Scale	x	x			x	x	x	x	x
Dysautonomia Assessment (e.g., COMPASS-31)		x					x	x	x

Target Day	-28	-7	0	1	15	30	90	180	360
Visit Name	Screen	Baseline	Intervention	Phone FU	2W	1M	3M	6M	12M
Visit Window	-28 to -8	-21 to -1	N/A	+1	+/-3	+/-5	+/-14	+/-14	+/-28
DSQ-PEM		x		x	x	x	x	x	x
WHO-DAS		x					x	x	x
Neurocognitive assessment (e.g., NIH Toolbox)		x					x	x	x
6MWT		x			x	x	x	x	x
Safety Outcomes									
AE Review	x	x	x	x	x	x	x	x	x
Safety Labs			x		x				
Real-time laboratory tests									
Pregnancy testing	x		x				x		
Complete metabolic panel	x		x		x				
CBC/diff	x		x		x				
Coagulation studies Within 6 months of Screen	x								
Hep B surface antigen Within 6 months of Screen	x								
Hep C antibody Within 6 months of Screen	x								
Hep C RNA (if Ab positive) Within 6 months of Screen	x								
Plasma HIV RNA (if HIV+) Within 2 months of Screen	x								
C-reactive protein		x	x		x	x	x	x	x
Erythrocyte sedimentation rate		x	x		x	x	x	x	x
D-dimer		x	x		x	x	x	x	x
Fibrinogen		x	x		x	x	x	x	x
SARS-CoV-2 PCR or Ag test	x	PRN	PRN		PRN	PRN	PRN	PRN	PRN
Stool collection (optional)		x				x		x	x

Target Day	-28	-7	0	1	15	30	90	180	360
Visit Name	Screen	Baseline	Intervention	Phone FU	2W	1M	3M	6M	12M
Visit Window	-28 to -8	-21 to -1	N/A	+1	+/-3	+/-5	+/-14	+/-14	+/-28
Post-hoc laboratory tests									
SARS-CoV-2 antibody testing		x							
Biospecimen storage	x	x	x		x	x	x	x	x
Markers of viral persistence	x	x	x		x	x	x	x	x
Markers of inflammation		x	x		x	x	x	x	x
PK analyses 			x 		x	x	x	x	x

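### The anemia hold on study blood draws lifts when either Hgb or HCT recovers, although the other value may still meet the hold trigger; the release needs *and*, not *or*

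*Combined protocol and SAP*

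**What the plan says.** The phlebotomy paragraph of protocol Section 2.3.2 (Protection Against Risk) sets both ends of a hold.

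- **Trigger:** if "hemoglobin falls below 9 grams/deciliter (g/dl) or HCT falls below 27%, we will draw 5 mL of blood to check safety labs". Either low value is enough.
- **Release:** apart from blood for safety labs, the participant "will not have more blood drawn until the Hgb rises above 9 g/dl or the HCT rises above 27" percent. Either recovered value is enough.

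The same paragraph gives the investigator discretion: "If the investigator feels that an individual is at significant risk for anemia, the amount of blood collected will be reduced". It also requires a check for signs and symptoms of anemia at each visit and leaves the timing of the blood count (CBC/diff) to the Schedule of Events. Section 9 makes that schedule decisive: "The Schedule of Events will serve as the final resource for guiding study activities". Section 2.3.1 adds a volume limit that counts LIINC blood as well: "No more than 500 mL (2 cups) of blood will be drawn over any two-month period".

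In Appendix 1 the CBC/diff row is marked at Screening, D0 and D15. Other blood tests, for example the "C-reactive protein" row, continue through D360.

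**The concern.** A stopping rule and its release should be complements: if either of two findings stops an activity, both must clear before it restarts. Here the two clauses use the same connective, so they overlap. Staff who follow the release clause literally could resume research draws in a participant who still meets the protocol's own criterion for stopping. The stake is participant safety in a study with repeated blood collection. No efficacy or safety comparison between arms depends on it.

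**Working it through.** No sample size or test is involved, so the check is one of logic.

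**Inputs.** Trigger (Section 2.3.2): Hgb < 9 g/dL or HCT < 27%. Release (same paragraph): Hgb > 9 g/dL or HCT > 27%. Both values come from the complete blood count (Section 9.2.1). Values exactly at a limit are left aside.

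**Step 1: the two clauses side by side.** The example values are assumed.

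| Hgb (g/dL) | HCT (%) | Trigger met | Release as written | Release with *and* |
|---|---|---|---|---|
| 8.8 | 26.0 | yes | no | no |
| 8.8 | 27.5 | yes | yes | no |
| 9.2 | 26.5 | yes | yes | no |
| 9.2 | 27.5 | no | yes | yes |

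As written, trigger and release are both met in the two discordant rows. With *and*, they are never met together.

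**Step 2: the narrower reading.** Suppose that only a value which had fallen can rise above its limit. Discordant pairs with a single fallen value then stay on hold. The case with both values low remains. Assumed sequence:

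- First test: Hgb 8.5, HCT 26.0. Since 8.5 < 9 and 26.0 < 27, the hold starts.
- Repeat test: Hgb 8.8, HCT 27.3. HCT had fallen and has risen above 27, so the release is met; 8.8 < 9, so the trigger is still met.

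The conflict therefore survives the reading most favorable to the text.

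**Step 3: how wide the overlap is.** The two limits coincide only when Hgb divided by HCT (as a fraction) equals 9 / 0.27 = 33.3 g/dL. The documents give no such ratio, so a range of 31 to 36 is assumed.

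- Ratio 31: at HCT 27%, Hgb = 31 × 0.27 = 8.37. Overlap for Hgb 8.37 to 9.0, a width of 0.63 g/dL.
- Ratio 32: 32 × 0.27 = 8.64. Overlap for Hgb 8.64 to 9.0, a width of 0.36 g/dL.
- Ratio 35: at Hgb 9, HCT = 9 / 0.35 = 25.7%. Overlap for HCT 25.7% to 27%.
- Ratio 36: 9 / 0.36 = 25.0%. Overlap for HCT 25.0% to 27%, a width of 2.0 points.

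These bands lie close to the limits.

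**Step 4: schedule count, for context.** Blood is drawn at 8 visits (Screening, Baseline, D0, D15, D30, D90, D180, D360). CBC/diff is scheduled at 3 of these, and at none of the 4 after D15.

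**The case against.** The best defense is that the release sentence mirrors the trigger and was meant to say that whichever value fell must recover. That is a natural reading and probably the intent, but the text does not say it, and Step 2 shows that it leaves the case of two low values open.

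It can also be said that the repeat Hgb of 8.8 itself meets the trigger, so the paragraph is contradictory rather than a clear instruction to resume. That stands, and the point claims no more. A safety rule should still not leave staff to choose between two of its own clauses.

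The objections on scale are sound. Exclusion 15 removes Hgb below 9 g/dL, inclusion 2 requires membership of LIINC, which does not take people with chronic anemia, the volume cap applies, and the investigator may reduce collection. The two overlapping rows out of four in Step 1 describe the logic and say nothing about frequency.

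A reader might go further and infer from Appendix 1 that the hold has no input after D15, and that the missing later blood counts are an error. The documents do not support that:

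- The D15 result is available before the D30 draw, and later draws are 60, 90 and 180 days apart at target (90 − 30, 180 − 90, 360 − 180).
- Signs as well as symptoms of anemia are checked at each visit, and Section 10.6 allows unscheduled laboratory tests.
- The documents do not say whether LIINC visits include a blood count, so it is unknown whether Hgb goes unmeasured.
- Anemia symptoms do overlap with Long COVID: "Symptoms of anemia include tiredness, weakness, and dizziness", while inclusion 4a accepts "systemic symptoms (e.g., fatigue, chills, post-exertional malaise") and, separately, dizziness. But Sections 9.1.6 and 9.1.7 record as an adverse event any symptom worse than the participant had before, so change is judged against the participant's own history.

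How often to repeat the blood count is thus a choice the authors were entitled to make.

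**Conclusion.** The release rule in Section 2.3.2 is wrong as written and contradicts its own trigger. The conclusion follows from the text alone and holds on both the literal and the narrower reading. It is minor. That the conflict would seldom arise rests on the assumption that Hgb and HCT, taken from one blood count, usually move together, and on the entry criteria and volume cap. The documents give neither the volume per draw nor the chance of Hgb falling below 9 g/dL, so no frequency is estimated. Sample size, power, type I error and the comparison between arms are untouched. The schedule of blood counts after D15 is not part of the error.

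**What to change.** In Section 2.3.2, replace *or* with *and* in the release clause, so that draws beyond safety checks resume only when Hgb is above 9 g/dL and HCT is above 27%. This is one word, with no added test or visit. As a protocol change it needs IRB approval under Section 17.1, and it could be included in the next amendment.

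Optional, as a suggestion only: mark CBC/diff at the existing D30 and D90 draws. D30 is the first visit whose count would reflect the D15 draw, and D90 the first that would reflect the D30 draw. The D90 mark would also cover discontinuation visits after D15, which use the D90 assessments (Section 10.7). The cost is 30 × 2 = 60 tests. At the 5 mL that Section 2.3.2 uses for a safety check, that is 2 × 5 = 10 mL per participant, each test taking 5 / 500 = 1% of the two-month cap.
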